Inclusion Criteria	Subjects enrolled in this study must meet all of the following inclusion criteria (based on investigator judgement): 
 1. Subject has chronic intractable pain of the trunk and/or limbs (VAS ≥ 6 cm in at least one of the regions intended to be treated with SCS). 2. Subject is willing and capable of giving informed consent and able to comply with study-related requirements, procedures, and visits. 3. Subject has trunk and/or limb pain such that lead placement will be in the lumbar to cervical region.
Exclusion Criteria	Subjects enrolled in this study must not meet any of the following exclusion criteria (based on investigator judgement): 
 1. Subject is unable to operate the system. 2. Subject is an unsuitable surgical candidate. 3. Subject has a condition currently requiring or likely to require the use of diathermy. 4. Subject has another implantable stimulator such as demand type pacemakers or cardioverter defibrillator. 5. Subject is <18 years old. 6. Subject is pregnant or nursing.

	
 7. Subject is allergic, or has shown hypersensitivity, to any materials of the neurostimulation system which come in contact with the body. 8. Subject is involved in an injury claim under current litigation or has pending/approved worker's compensation claim. 9. Subject has prior experience with SCS. 10. Subject is being treated with electroconvulsive therapy (ECT) or transcranial magnetic stimulation (rTMS).
Investigation Sites	Up to 25 US sites.
Enrollment	Up to 300 subjects (enrollment defined as trial procedure). Enrollment is anticipated to take 36 months.

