5 STUDY DESIGN

This study is a prospective, multicenter, single-arm study designed to examine ECAP-controlled, closed-loop stimulation with the Evoke System to treat patients with chronic pain of the trunk and/or limbs.

Subjects with chronic, intractable pain of the trunk and/or limbs will be screened for participation in this study. Subjects who provide informed consent and meet the study eligibility criteria undergo a trial procedure and will be enrolled. Following the trial phase subjects may receive a permanent implant and be followed up at 1-, 3-, 6-, 12-, 18-, and 24-months following the permanent implant.

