8.3 Enrollment

Subjects who provide informed consent and meet eligibility criteria will be considered enrolled at the time of the trial procedure.

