8.4 Temporary SCS Trial Phase

Before permanent implant of the Evoke System, subjects will undergo a trial stimulation phase with the external stimulator attached to one or two Evoke leads. The procedure will be performed in accordance with standard of care and the Evoke IFU. The device will be programmed for pain coverage in accordance with the Evoke IFU. Timing of post-procedure programming will occur at the discretion of the Investigator.

The trial will last up to 30 days (typically 1 week) to determine if the subject will proceed to the permanent implant. Subjects may have multiple visits during the trial phase in order to optimize stimulation settings. The following data will be collected during the trial phase:

Trial Procedure/Post-procedure:

- Trial procedure data
- X-rays (AP and lateral) during the procedure
- Posture change measurements (to be collected at least once post-procedure through Trial End)
- Neurophysiological measurements (to be collected at least once post-procedure through Trial End)
- Device programming

Trial End:

- Study Pain Assessment
- PROMIS-29+2
- PROMIS-10 Global
- POMS 2-A Short
- PGIC & Patient Satisfaction
- Stimulation characteristics
- Posture change measurements (to be collected at least once post-procedure through Trial End)
- Neurophysiological measurements (to be collected at least once post-procedure through Trial End)
- X-rays (AP and lateral) prior to lead pull
- Lead pull procedure

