8.5 Implant Procedure/Post-procedure

Subjects will be approved to undergo implantation of the Evoke System if the subjects' trial was successful based on physician and subject determination.

The permanent implant will involve the implantation of the Evoke stimulator and one or two Evoke leads. The implant procedure will be performed in accordance with standard of care and the IFU, and programming will be performed in accordance with the IFU. Timing of post-procedure programming will occur at the discretion of the Investigator, prior to the 1-month follow-up visit.

The following data will be collected during the implant procedure/post-procedure:

- Implant procedure data
- X-rays (AP and lateral) during the procedure
- X-rays (AP and lateral) post-procedure, prior to 1-month follow-up
- Neurophysiological measurements (optional)
- Device programming

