9.2.2 Adverse Event Reporting

Investigators are required to report all AEs from the time of consent (except as outlined below). If an AE leads to multiple outcomes that sequentially worsen, only the worst AE will be reported.

Investigators shall report AEs to the Sponsor, and to their reviewing IRB per the IRB's reporting requirements. Investigators are required to report UADEs to the Sponsor and their reviewing IRB as soon as possible, but in no event later than 10 working days after the Investigator first learns of the effect, per 21 CFR 812.150 (refer to section 13.7.2 for Investigator reporting requirements).

AE reporting exceptions:

- AEs that would be reasonably expected to be associated with any surgical procedure (e.g., anesthesia associated symptoms, surgical site pain, post-procedure pain) will not be required to be reported as AEs unless, in the opinion of the Investigator, the nature and/or severity is outside of what is typical for SCS procedures and recovery.
- Lack of efficacy, by itself, does not constitute an AE since failure to receive therapeutic benefit is an issue of efficacy, not safety.
- Loss of therapy/stimulation does not constitute an AE unless an untoward medical occurrence results.
- A subject's perception of the stimulation induced feeling of stimulation sensation is called paresthesia. There are well-known challenges associated with optimizing SCS such as changes in stimulation intensity and stimulation in unwanted areas. These will not be reported as AEs unless the Investigator determines the nature and/or severity is outside what is typical for neurostimulation.
- Temporary changes in symptoms and stimulation that are alleviated with programming will not be reported as AEs unless the Investigator determines the nature and/or severity is outside what is typical for neurostimulation.

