12 RISK ANALYSIS

12.1 Potential Risks

Risks associated with the Evoke System are similar to those of other open-loop SCS systems, which are generally minor. All medical procedures involve some risk of injury, including death. Other anticipated risks associated with the Evoke System are listed in this protocol or found in the literature, post-market surveillance data (e.g., FDA Manufacturer and User Facility Device Experience (MAUDE) database), and device labeling for SCS systems. Please refer to the current Evoke IFUs for the most up-to-date risks associated with the Evoke System.

In addition to the general surgical risks, potential risks to subjects associated with implantation and use of the Evoke System include, but are not limited to:

- Undesirable changes in stimulation sensation and/or location
- Uncomfortable changes in stimulation (over and/or under stimulation)
- Persistent post-surgical pain at hardware implantation sites
- CLS migration, which may result in pain or difficulty in charging
- Seroma or hematoma at surgery sites
- Epidural hemorrhage, spinal cord injury and possible paralysis
- Lead migration from the location chosen at initial implantation resulting in stimulation changes
- Breakage of the lead or failure of other system components, which may result in loss of stimulation
- Rejection of, or allergic reaction to, the implanted components
- Infection that may require hospitalization with intravenous antibiotic therapy
- Cerebrospinal fluid (CSF) leakage
- Inadequate pain relief following system implantation
- Erosion of the lead or CLS through the skin
- Weakness, clumsiness, numbness or pain

Subjects may require surgery (including revision, explant, and replacement) as a result of any of the above.

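### An enrolled subject who is not implanted has the last scheduled safety evaluation at Trial End, the visit that includes the lead pull; no later contact, exit status or end of AE collection is set for this branch

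*Combined protocol and SAP*

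**What the plan says.** - **Enrolment.** Section 8.3 says that consenting, eligible subjects "will be considered enrolled at the time of the trial procedure". The Enrollment row of section 1 agrees: "Up to 300 subjects (enrollment defined as trial procedure". A subject whose trial fails is thus an enrolled subject, not a screen failure.
- **Trial phase.** Section 8.4 has one or two leads in place for up to 30 days, typically a week. The list of Trial End activities finishes with "Lead pull procedure".
- **Moving to implant.** Under section 8.5 a subject is implanted only if the "trial was successful based on physician and subject determination".
- **Follow-up.** Section 5 says: "Following the trial phase subjects may receive a permanent implant and be followed up at 1-, 3-, 6-, 12-, 18-, and 24-months following the permanent" (last word of the sentence cut). Section 8.6 and Table 4 use the same six visits.
- **Safety checks.** The Safety row of Table 4 is marked in all ten visit columns; its footnote covers adverse events, device deficiencies and protocol deviations.
- **AE reporting.** Section 9.2.2: "Investigators are required to report all AEs from the time of consent (except as outlined below". A start is given, but no end.
- **Exit.** Section 8.9 recognises two routes out for enrolled subjects, completion and early withdrawal. For early withdrawals it commits to trying to obtain safety data, without a method or date.
- **Use of the data.** Section 11.3 will report AE incidence, including by relatedness to the procedure. Section 2.5 gives continuing safety evidence as one reason for the study.

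**The concern.** The trial phase is an invasive procedure in its own right, and all who undergo it count as enrolled. Yet the calendar after Trial End exists only for those who go on to implant. The risks in section 12.1 include "Epidural hemorrhage, spinal cord injury and possible paralysis" and "Infection that may require hospitalization with intravenous antibiotic therapy", as well as CSF leakage and hematoma. The plan does not say when such events appear, and nothing in it supports assuming that all would be evident by the time the leads come out.

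What is at stake is the completeness of the AE summary. If trial-only subjects are in the denominator for procedure-related AEs, they contribute to it with no scheduled question after lead removal. Sites may also close AE collection for them at different times, because no exit point is stated for this branch.

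**Working it through.** **1. The plan's own figure.** Section 11.1 claims a half-width of about ±6% for n = 300 at 50% incidence. The exact (Clopper-Pearson) 95% interval for 150/300 is 44.20% to 55.80%, so the half-width is (55.80 − 44.20)/2 = 5.80%. The claim reproduces and is not in dispute. It matters here only because section 1 counts the 300 at the trial procedure, so the number includes subjects who are never implanted.

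**2. The two branches in Table 4.**

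| Scheduled safety evaluation | Implanted | Not implanted |
|---|---|---|
| Baseline | yes | yes |
| Trial procedure | yes | yes |
| Trial End (includes lead pull) | yes | yes |
| Implant procedure | yes | none |
| Months 1, 3, 6, 12, 18, 24 | yes (6) | none |
| Total | 10 | 3 |
| After the Trial End visit | 7 | 0 |

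**3. Whether another provision fills the empty cells.**

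- *Section 9.2.2.* With no end date, a later event that the site learns of is still reportable. The section does not require the site to ask.
- *Section 8.9, early withdrawal.* If a failed trial counts as early withdrawal, an attempt to collect safety data is promised, but with no contact, timing or window. If it counts as completion, the sentence does not apply. The protocol does not say which.
- *Section 8.9, lost to follow-up.* The three contact attempts are triggered by a missed scheduled visit. After Trial End a trial-only subject has none left to miss.
- *Section 13.8.1.* Sponsor representatives may contact subjects about stimulation and device function. That is not AE ascertainment, and after lead pull a trial-only subject has no stimulation to check.

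None of these sets a contact after lead pull.

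**4. Size of the group.** The documents give no trial-failure rate. With an assumed share f, the number is m = 300 × f. If no late event were recorded among m fully observed subjects, the upper limit of the exact two-sided 95% interval would be 1 − 0.025^(1/m).

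| Assumed f | m | Upper limit with 0 events |
|---|---|---|
| 10% | 30 | 11.6% |
| 20% | 60 | 6.0% |
| 30% | 90 | 4.0% |

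Even with complete ascertainment this subgroup is only modestly informative. Without it, a zero count could not be read even that far. The expected number of late events would also need an event rate, which the documents do not give, so none is claimed.

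**5. What the existing window would mean.** The 1-month window is 30 days, −14/+21. Counted from lead pull, it runs from day 30 − 14 = 16 to day 30 + 21 = 51.

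**The case against.** The strongest reply is that the plan already covers this. AE reporting is open-ended, and a subject who leaves before any follow-up visit fits early withdrawal at least as well as completion, so safety data would be sought. Sites must also keep complete medical records as source (section 13.7.1). On that view a one-sentence clarification is enough, and a required contact is partly preference. The study is descriptive, plans no formal hypothesis tests and has no separate trial-phase safety estimate. Section 12.4 calls complication rates very low.

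Part of this stands. It rules out several stronger readings that a reader might infer:

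- *Later events surface only if the subject volunteers them.* Not supported: reporting stays open, and records and withdrawal follow-up are other routes.
- *The procedure will look safer than it is.* Not shown: no event rate is given, and the extent of unsolicited reporting is unknown. Under-ascertainment is possible, not established.
- *Trial-only subjects exit at lead pull.* The protocol does not say so; it gives no exit point for them.
- *Zero days of observation against as long as the 24-month visit.* That is not like for like, since the longer period follows a permanent implant. The comparable interval, lead pull to implant, is not stated.
- *The same gap exists after explant.* Section 8.8 already collects AEs there.

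What the reply does not supply is a contact, a window or an exit status. Section 12.2 relies on close monitoring of subjects to limit risk, and a branch with no scheduled contact after lead removal sits poorly with that. The Appendix A consent form and the Data Management Plan were not available for this check. If either sets such a contact, the protocol need only be aligned with it.

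**Conclusion.** The point holds as a gap in scheduled ascertainment, not as a bar on reporting. For an enrolled subject who is not implanted, the last scheduled safety evaluation is at Trial End, and exit status and the end of AE collection are undefined. Procedure-related AE incidence may be under-ascertained in this subgroup. An assumed non-implant share of 10% to 30% gives 30 to 90 of 300 subjects; that share is not in the documents, and the number of events affected cannot be estimated from them. The consequence for the AE summary also assumes that trial-only subjects are in its denominator, which section 11.3 does not specify. This is a worthwhile, inexpensive improvement to data collection and does not undermine the study.

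**What to change.** In Table 4 and sections 8.4 and 8.9, state that subjects who do not proceed to implant remain in the study for one safety contact after lead pull, telephone allowed. The existing 1-month window, counted from lead pull, would serve. Collect AEs through that contact and complete the exit form then. State also whether a failed trial is recorded as completion or early withdrawal.

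The purpose is complete AE ascertainment, not clinical management. A contact on days 16 to 51 records events after the fact; it is not a means of early detection.

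The cost is one call by existing staff on the existing safety form for each such subject (30 to 90 under the assumption above), with no added procedure or enrolment. Exit comes about a month later for these subjects, and a few contacts will be lost.

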6 STUDY POPULATION

6.1 Study Sites

Study subjects will be enrolled at up to 25 US sites.

6.2 Inclusion Criteria

Subjects enrolled in this study must meet the following inclusion criteria, as determined by the Investigator:

1. Subject has chronic intractable pain of the trunk and/or limbs (VAS ≥ 6 cm in at least one of the regions intended to be treated with SCS).
2. Subject is willing and capable of giving informed consent and able to comply with study-related requirements, procedures, and visits.
3. Subject has trunk and/or limb pain such that lead placement will be in the lumbar to cervical region.

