8 STUDY PROCEDURES

8.1 Visit Schedule

Table 4. Required Protocol Assessments

	Screening			Temporary SCS Trial Phase			Permanent SCS Implant Phase			
	Baseline	Trial Procedure/ Post-procedure	Trial End (≤30 days)	Implant Procedure (Day 0)/ Post-procedure	1 Month (30 days -14 days, +21 days)	3 Month (90 days ± 21 days)	6 Month (180 days ± 30 days)	12 Month (365 days ± 60 days)	18 Month (545 days ± 90 days)	24 Month (730 days ± 90 days)
Protocol Assessments	X									
Informed Consent & Inclusion/Exclusion	X									
Baseline Evaluation	X									
Procedure ¹		X	X	X						
Imaging ²		X	X	X						
Investigator Evaluation										
Study Pain Assessment	X		X		X	X	X	X	X	X
Medications	X	X	X	X	X	X	X	X	X	X
Safety ³	X	X	X	X	X	X	X	X	X	X
Subject Questionnaires										
PROMIS-29+2	X		X		X	X	X	X	X	X
PROMIS-10 Global	X		X		X	X	X	X	X	X
POMS 2-A Short	X		X		X	X	X	X	X	X
PGIC & Patient Satisfaction			X		X	X	X	X	X	X
Stimulation Characteristics			X		X	X	X	X	X	X
Neurophysiological Data										
Posture Change Measurements		X			X	X	X	X	X	X
Neurophysiological Measurements ⁴	X		O	X	X	X	X	X	X	X
Programming ⁵	X		X	O	O	O	O	O	O	O

Additional Optional Assessments ⁶	O	O	O	O	O	O	O	O	O	O	O

X = Required; O = Optional

¹ Trial procedure, trial end lead pull procedure, or permanent implant procedure.

² X-rays (AP and lateral) will be taken during the trial, implant, and revision/replacement procedures per standard of care. Additionally, X-rays (AP and lateral) are required prior to lead pull at Trial End and prior to the 1-month visit post-permanent implant. Fluoroscopy may substitute for X-ray. Additionally, imaging (e.g., X-ray, CT) may be taken at any time during the study in order to evaluate potential AEs, as needed and determined by the physician.

³ Includes evaluation for potential adverse events, device deficiencies, and protocol deviations.

⁴ Neurophysiological measurements may occur over more than one visit. Neurophysiological measurements for the trial and implant procedure need not be collected on the procedure date; they may be collected prior to and including trial end or the 1-month visit window, respectively. At follow-up, activation plots must be collected on the follow-up visit date; however, other neurophysiological measurements (e.g., conduction velocity, chronaxie, rheobase) may be collected any time within the visit window.

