8.2 Screening/Baseline Evaluation

Potential study subjects will be identified and informed of the study. Subjects who provide informed consent for study participation (refer to section 13.2.2) will complete the study-specific baseline assessments. Medical records documenting the condition of the subject, including relevant previous medical history and results of diagnostic tests, will be obtained. Data collected during screening/baseline include:

- Determination of subject study eligibility (inclusion/exclusion criteria)
- Demographics, medical history, and physical examination
- Study Pain Assessment (including DN4 and pain etiology/pathophysiology)
- PROMIS-29+2
- PROMIS-10 Global
- POMS 2-A Short

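### Does taking the VAS baseline in the same evaluation that applies the 6 cm entry rule call for a second pre-treatment reading?

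*Combined protocol and SAP*

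**What the plan says.** Inclusion criterion 1 (section 6.2) requires "VAS ≥ 6 cm in at least one of the regions intended to be treated with SCS", as judged by the investigator. It does not say which VAS reading decides.

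Section 8.2 lists "Determination of subject study eligibility (inclusion/exclusion criteria") and "Study Pain Assessment (including DN4 and pain etiology/pathophysiology") among the data of the same screening/baseline evaluation. The Study Pain Assessment contains a VAS for each shaded region (section 7.1). Table 4 in section 8.1 marks both the "Informed Consent & Inclusion/Exclusion" row and the Study Pain Assessment at Baseline. The next Study Pain Assessment is at Trial End, after stimulation has begun (section 8.4). No run-in or repeat baseline is scheduled.

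Section 5 describes a single-arm study, so there is no concurrent control. Under section 8.5 a subject goes on to implant if the "trial was successful based on physician and subject determination"; the 1- to 24-month visits follow from there.

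Section 11.2 names no specific outcome variable. Section 11.3 says that no formal hypothesis tests are pre-planned. It allows one-sample t-tests and exploratory models with nominal, unadjusted p-values. The sample size in section 11.1 rests on the precision of an incidence.

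**The concern.** Selecting people because a noisy measurement lies above a cut-off selects, in part, for positive error. A second measurement is then lower on average with no treatment at all. A randomised control arm would show the same fall and cancel it; this study has none.

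A second selection may add to the first. If trial success is judged by the fall from the same baseline reading, subjects whose baseline erred upwards are more likely to be implanted and followed to 24 months.

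At stake is the credibility of a before-after VAS change. If it were tested against zero by a one-sample t-test, the artefact alone could often give p < 0.05.

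**Working it through.** **The plan's own figure.** The only quantitative claim in section 11 is a half-width of about 6 points with 300 subjects at 50% incidence. For 150/300 the exact 95% interval is 44.2% to 55.8%, half-width 5.80 points. The claim reproduces, and it does not depend on VAS change.

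**Inputs.** The cut-off of 6 cm comes from section 6.2 and the cap of 300 subjects from section 1. The readable text gives no VAS mean, SD or test-retest correlation. Section 2.4, on prior experience, is not legible in the copy available, so this absence is no criticism of the plan. Assumed: unselected mean 6.5 to 7.5 cm, SD 1.5 to 2.0 cm, correlation r 0.6 to 0.8, one region, and the same reading used for entry and baseline.

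**Artefact at Trial End, all enrolled, no treatment effect.** With a = (6 − mean)/SD and λ = φ(a)/(1 − Φ(a)), the expected fall is (1 − r) × SD × λ.

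- Midpoint (7.0, 1.75, 0.7): a = −0.571, λ = 0.3388/0.7161 = 0.473. Fall = 0.3 × 1.75 × 0.473 = 0.248 cm. Selected baseline mean = 7 + 1.75 × 0.473 = 7.83 cm, so the fall is 0.248/7.83 = 3.2% of it.
- Smallest (7.5, 1.5, 0.8): 0.086 cm.
- Largest (6.5, 2.0, 0.6): 0.517 cm.
- A fall of 50% or more with no true change: about 0.2% of subjects at the midpoint, at most about 1.7% over the grid.

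**One-sample t-test against zero, zero true effect, n = 300.** The variance of change is (1 − r)² × SD² × (1 + aλ − λ²) + SD² × (1 − r²). At the midpoint this is 0.139 + 1.562 = 1.701, so the SD is 1.304. The noncentrality is 0.248/(1.304/√300) = 3.30. The probability of a nominally significant improvement is 0.91; over the grid it runs from 0.36 to above 0.99.

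**Implanted subjects.** This is a simulation at the midpoint, with VAS clipped to 0–10. It assumes a true effect of 4 cm (SD 2) and, for illustration only, success defined as a 30% or 50% fall from the baseline in use. Bias is the baseline minus an independent pre-treatment reading. The last row assumes zero effect and implant after any fall.

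| Setting | Screening reading as baseline | Second reading, independent errors | Second reading, errors correlated 0.7 |
|---|---|---|---|
| All enrolled, Trial End | 0.25 cm | 0.00 cm | 0.17 cm |
| Implanted, 30% rule | 0.34 cm | 0.10 cm | 0.27 cm |
| Implanted, 50% rule | 0.40 cm | 0.13 cm | 0.33 cm |
| Implanted, zero effect | 0.64 cm | 0.51 cm | 0.61 cm |

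**Region.** Entry needs only one region at or above 6 cm. With two regions at the midpoint, and errors independent between regions, the artefact is 0.06 to 0.08 cm for a pre-specified region or the average. It is 0.41 to 0.53 cm if the region highest at baseline is tracked.

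**The case for a change.** The best case for a change is that it is cheap: one short VAS at the existing trial-procedure visit before lead placement, named as the baseline in section 11. If the two pre-treatment errors were independent, the entry artefact at Trial End would disappear. Section 11.3 does allow p-values, and readers of a single-arm report may take p < 0.05 as benefit. The training in section 13.5.1 may reduce noise but does not separate the entry reading from the baseline. The choice among regional scores is open and affects the size.

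The mechanism and the arithmetic stand. The case for the remedy is weaker:

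- Errors in two readings taken before treatment by the same patient may well be correlated. At 0.7 the gain among implanted subjects is 0.07 cm (0.34 to 0.27, or 0.40 to 0.33), and 0.03 cm with zero effect (0.64 to 0.61).
- A reading on the day of the procedure may be atypical, and a mid-study change would leave two baseline definitions in one cohort. It would also need an amendment approved by the sponsor and the IRB (sections 13.2.1 and 13.10) at up to 25 sites.
- The high rejection rates need VAS change to be the tested variable, zero to be the null value and the true effect to be zero. The plan states none of these. In any uncontrolled before-after study, p < 0.05 against zero does not by itself show benefit, and a second reading would not alter that.

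Naming the baseline adds little, since Table 4 and section 8.2 leave only one candidate. Stating the region would be useful, but analysts can do so when they report. They also have a cross-check at no cost: the 0–10 pain-intensity item of PROMIS-29+2 (section 7.3) is scheduled at baseline, Trial End and every follow-up visit and is not the entry measure. It is affected indirectly, through same-day error and selection at implant.

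**Conclusion.** The concern is a fair caution about interpretation, not a fault in the plan. If the qualifying reading is the baseline, VAS change could be overstated by roughly 0.1 to 0.5 cm (0.25 cm at the midpoint) for all enrolled subjects. For implanted subjects the midpoint figure is 0.3 to 0.4 cm if trial success is judged from that reading and the true effect is about 4 cm. These figures rest on assumed means, SDs and correlations, and on an identity of readings that the protocol does not state. They explain little of a large reduction and almost nothing of a 50% responder rate.

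The stated aim is to characterise outcomes in a real-world population, with no formal test and with precision set for an incidence. One baseline in routine practice is a fair trade-off for that aim, and a second reading would give a partial and possibly very small gain. The descriptive conclusions stay sound provided that the report says which region is analysed and does not present a nominal p-value against zero as proof of benefit.
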